Double-Blind Randomized Controlled Trial Comparing Two Standardized Radial Pressure Wave Techniques Versus Pain-Site Guided Therapy in Patients With Knee Osteoarthritis: Four-Month Outcomes

NCT number: NCT06622512

Document date: September 4th, 2024

Introduction

Osteoarthritis (OA) is the most common musculoskeletal joint disorder in adults worldwide, with the knee being the most frequently affected region.^{1,2,3} Knee osteoarthritis (KOA) is a chronic and progressive joint disease characterized by the loss of articular cartilage, resulting in damage to the subchondral bone, synovial structures, and surrounding soft tissues.^{3,4,5} This chronic-degenerative condition is associated with a high health burden for patients and implications for healthcare systems. It is considered the leading cause of permanent disability in individuals over the age of 65, with an estimated global prevalence affecting around 365 million people.⁶ In Mexico, the prevalence of KOA is 2.3% in the adult population, and within the Mexican Institute of Social Security, it ranks among the top 10 reasons for primary care visits.^{3,4,5}

KOA is a multifactorial disease in which various harmful agents can initiate and perpetuate damage to the articular cartilage, subsequently triggering responses in the synovial membrane and subchondral bone. When the balance between cartilage matrix formation and degradation is disrupted—favoring degradation beyond the system's compensatory capacity—matrix breakdown ensues, ultimately leading to OA.¹² The main risk factors include age over 50 years, obesity, repetitive activities, joint instability, and malalignment.^{1,3,4,5}

Extracorporeal shock wave therapy (ESWT) is a non-invasive therapeutic procedure aimed at producing analgesia and facilitating the healing of musculoskeletal conditions. There are two types of extracorporeal shock waves: focused shock waves and radial shock waves—also known as radial pressure waves—which can be generated using electrohydraulic, electromagnetic, or piezoelectric sources.^{7,8} The mechanism of action involves the distribution of pressure, energy flux density, and total acoustic energy to produce microscopic interstitial and extracellular responses that promote tissue regeneration. The effects of radial pressure wave therapy (RPWT) include analgesia, protein synthesis, neovascularization, and cellular proliferation.^{9,10,11,12}

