Sample size calculation: The primary outcome for sample size determination was pain intensity (NPRS). Using a two-tailed α of 0.05, 80% power ($\beta = 0.20$), an expected clinically relevant effect size of 2.0, and a standard deviation of 2.1 (based on prior literature), the required sample size per group was 17 participants. Anticipating a 20% attrition rate, we adjusted the sample to 23 participants per group to preserve statistical power. Therefore, a total of 69 participants were recruited and equally distributed across the three study arms.

Intervention Groups:

- Control group: Patients received 3 weekly RPWT sessions in the supine position with the knee flexed 30°–60°. A total of 2000 shocks per session were applied at the two most painful palpated sites (based on physical examination), using a fixed frequency of 10 Hz and an intensity of 2.0 bar. At the final session, participants were trained to continue with a four-week home-based physical therapy program including superficial thermotherapy, stretching, strengthening, proprioceptive retraining, and general recommendations.
- Experimental group 1: Patients received 3 weekly RPWT sessions in the same position. A total of 2000 shocks were applied to the medial joint line using a non-fixed frequency (10 Hz) and intensity of 2.0 bar. At the final session, they were instructed to follow the same four-week home rehabilitation program as described for the control group.
- Experimental group 2: Patients received 3 weekly RPWT sessions with 2000 total shocks distributed equally over the medial (1000 shocks) and lateral (1000 shocks) joint lines. Frequency was non-fixed (10 Hz), and intensity was 2.0 bar. The same four-week home-based therapy program was prescribed after the third session.

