When the assumption of sphericity is violated, the Huynh–Feldt correction will be applied. Post hoc analyses will include:

- Bonferroni-adjusted pairwise comparisons for within-subject effects.
- Tukey's Honestly Significant Difference (HSD) test for between-group comparisons.

- Homogeneous subset analyses to identify clusters of similar treatment response profiles.

Effect size and power: Partial eta squared (η^2) will be reported to estimate the effect size. Observed power ($1-\beta$) will be documented where appropriate.

Statistical significance: A two-tailed p-value of ≤ 0.05 will be considered statistically significant for all analyses.

References

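### Tukey HSD is valid for these three arms, but a closed step-down test keeps the same 5% family-wise limit and finds second and third differences more often

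*Combined protocol and SAP*

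**What the plan says.** The statistical analysis plan sets a mixed repeated-measures ANOVA with a group factor of three levels: pain-site guided, medial line, and medial plus lateral lines. For the pairwise follow-up it names Tukey's "Honestly Significant Difference (HSD) test for between-group comparisons". It also lists homogeneous subset analyses without saying which procedure produces them. No step-down or closed procedure is named anywhere. The significance level is 0.05 two-sided throughout. Apart from p-values, the planned outputs are partial eta squared and observed power; simultaneous confidence intervals are not mentioned.

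The sample size section works from "an expected clinically relevant effect size of 2.0" and an SD of 2.1, states that "the required sample size per group was 17 participants", and allows for 20% attrition: "we adjusted the sample to 23 participants per group to preserve statistical power".

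**The concern.** Tukey HSD is a single-step procedure. It holds all three pairs to one enlarged critical value, even after the largest difference has been declared significant. With three arms that is stricter than 5% family-wise control requires, because at most one pairwise equality can still be true once the overall null is false.

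What is at stake is the second and third comparison. The title describes a trial "Comparing Two Standardized Radial Pressure Wave Techniques Versus Pain-Site Guided Therapy in Patients With Knee Osteoarthritis", so if both standardised techniques differ from pain-site guided therapy, the trial wants to show both differences. The sample size makes no allowance for multiplicity, so there is little power to spare.

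**Working it through.** **Inputs.** From the sample size calculation: difference 2.0, SD 2.1, two-sided 5%, power 80%, 17 per group, 20% attrition, 23 per group. From the SAP: three arms and Tukey HSD.

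**The plan's own figure.** n = 2 × (1.960 + 0.842)² × 2.1² / 2.0² = 17.3 per group, so the stated 17 is reproduced before rounding up to 18. Then 18/0.8 = 22.5, rounded up to 23. If 20% are lost from 23, about 18 remain (23 × 0.8 = 18.4). This is a two-group calculation at an unadjusted 5%.

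**The two procedures at 17 per arm (48 df).**
- HSD: every pair needs |t| above q(0.95; 3, 48)/√2 = 2.419.
- Step-down: the largest |t| needs to exceed 2.419. Only if it does, the other two pairs need |t| above t(0.975; 48) = 2.011.

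**Why step-down keeps the 5% limit.**
- If all three means are equal, any false rejection requires the largest |t| to exceed 2.419, which happens 5% of the time.
- If they are not all equal, at most one pair can be equal, since any two equalities imply the third. That single pair is never tested at more than 5%.

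The argument is special to three arms. With four or more, an unadjusted second step would not be protected in this way.

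**Why it never loses a Tukey rejection.** If HSD rejects a pair, that pair's |t| exceeds 2.419. The largest |t| then does too, and the pair also clears 2.011. This does not depend on the SD, the effect or the visit analysed.

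**Size of the gain.** For one pair at 17 per arm the noncentrality is 2.0/(2.1 × √(2/17)) = 2.777, and P(|T| > 2.419) on 48 df is 64%, the HSD power. The step-down figures come from simulating three equal arms with SD 2.1 and pooled variance, 1,000,000 trials per scenario. With one arm 2.0 points from the other two:

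| Evaluable per arm | Critical t, HSD | Critical t, second step | Power per real pair, HSD → step-down | Both real pairs, HSD → step-down | At least one rejection, either procedure |
|---|---|---|---|---|---|
| 17 | 2.419 | 2.011 | 64% → 71% | 49% → 63% | 79% |
| 18 | 2.414 | 2.008 | 67% → 74% | 53% → 67% | 82% |
| 23 | 2.398 | 1.997 | 79% → 85% | 68% → 80% | 91% |

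With means 0/1/2 at 17 per arm, each 1-point pair goes from 16% to 25% and the 2-point pair from 64% to 66%.

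**Error.** With all means equal, both procedures reject something in 5.0% of trials. With one pair equal and the third arm far away, that pair is falsely rejected in 1.9% of trials under HSD and 5.0% under step-down. In no simulated trial did HSD reject a pair that step-down did not.

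**Unequal arms.** Simple randomisation, elimination for a missed session and withdrawal make unequal evaluable arms likely. With an assumed 13/18/23 per arm, Tukey-Kramer statistics and the gate on the largest |t|, family-wise error stayed at or below 5%, and power for both pairs rose from 52% to 66%. The gate must be the largest t statistic, not the largest raw difference. With an assumed 21/19/14 and means 0/2/2, gating on the raw difference lost a Tukey rejection in 0.3% of trials.

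**The case against.** The strongest reply is that nothing here is wrong. Tukey HSD is a standard all-pairs procedure that suits a three-level factor and controls its error rate. That stands: a reader might infer that the SAP's test is invalid, and the documents give no support for it.

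A reader might also infer that power is given away for nothing. That goes too far, for three reasons.
- The chance of declaring at least one difference is the same under both procedures. The gain lies only in further pairs once one has been declared.
- A truly equal pair is rejected more often, at up to 5% instead of about 2%. That is within the limit, but it is a price.
- Single-step HSD comes with matching simultaneous intervals. This weighs less here because the SAP plans none.

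A third tempting inference is that the title asks only for two comparisons with pain-site guided therapy, so Dunnett's test should replace Tukey. Specific objective 1, however, asks whether the site of application affects outcome, and medial against medial plus lateral is a direct comparison of sites. All three pairs therefore belong, and Dunnett would demote one of them. Dunnett would also test both real differences only if the differing arm happened to be the control.

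Finally, 64% and 71% should not be read as this plan's power. The SAP's group effect averages over visits, apparently including baseline. Suppose a 2-point effect is present at two of three visits, with within-patient correlation ρ assumed to be 0.3 to 0.7. The averaged difference is then 2 × 2/3 = 1.33 and its SD is 2.1 × √((1 + 2ρ)/3). Power per real pair at 17 per arm becomes 37–55% with HSD and 43–62% with step-down. The levels fall, but the gain remains 6 to 7 points.

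**Conclusion.** The point holds as one of efficiency. For exactly three arms, step-down testing gated on the largest |t| has the same 5% family-wise limit as Tukey HSD and rejects everything HSD rejects. Those two properties follow from the argument above for equal arms; for unequal arms the error limit was also checked by simulation.

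The size of the gain rests on assumptions: one arm 2.0 points from the others, and an SD of 2.1 for the contrast analysed. On those terms it is about 7 points per real pair and about 14 points for finding both real differences at 17 or 18 per arm. It shrinks to 6 and 12 points if all 23 per arm are evaluable.

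The 5% limit covers the three pairs of one contrast on one outcome. Neither procedure deals with multiplicity across NPRS and WOMAC or across visits.

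**What to change.** Replace the Tukey line in the post hoc list with a closed step-down test for the three pairs:
- Compute the pairwise t statistics with pooled variance, in Tukey-Kramer form if evaluable arms are unequal.
- Compare the largest |t| with Tukey's critical value. Stop if it is not significant.
- If it is significant, test each of the other two pairs at unadjusted two-sided 0.05.
- Report Tukey simultaneous intervals for estimation, and note that they need not agree with the step-down p-values for the second and third pairs.
- State the single between-arm contrast to which this applies.

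The change is to SAP wording and needs no further patients or data. If the sponsor prefers to keep HSD, the SAP should give agreement between tests and simultaneous intervals as the reason, and should plan to report those intervals.

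### The homogeneous-subset analysis treats a non-significant Tukey comparison as similarity between arms, with no margin and no between-arm confidence interval to support that reading

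*Combined protocol and SAP*

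**What the plan says.** The Statistical analysis plan, under between-group analysis and interaction effects, specifies a mixed-design repeated-measures ANOVA with three arms. The post hoc list then gives Tukey's "Honestly Significant Difference (HSD) test for between-group comparisons" and, as its last item, "Homogeneous subset analyses to identify clusters of similar treatment response profiles".

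The next paragraph, Effect size and power, promises partial eta squared and says that observed power "will be documented where appropriate". It does not say what observed power is to be used for.

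The Sample size calculation section is written for detecting a difference: "Using a two-tailed α of 0.05, 80% power", with "an expected clinically relevant effect size of 2.0, and a standard deviation of 2.1". It concludes that "the required sample size per group was 17 participants", raised to 23 per group for attrition. No section gives an equivalence margin, an equivalence test or a confidence interval for a difference between arms.

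**The concern.** Two arms share a homogeneous subset when the range test does not reject equality of their means. That happens when the arms are alike, and also when they differ but the sample is too small to show it. The subset table cannot tell these apart, yet the plan describes its contents as similar response profiles.

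This bears on the main question. Specific objective 1 asks whether the site of application influences pain and function. All three arms receive active treatment with the same number of shocks, the same pressure and the same home programme, so a non-significant comparison is a plausible result. A shared subset could then be read as showing that site does not matter, while the data still allow a difference the plan itself calls clinically relevant.

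The other planned outputs do not guard against this. Partial eta squared gives neither direction nor size in NPRS points. Observed power is calculated from the same data and is a function of the p-value, so it carries no further information on whether a difference was missed. Descriptive means and SDs will show direction and approximate size, but not which differences the data exclude.

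**Working it through.** **Inputs.** From Sample size calculation: difference 2.0 NPRS points, SD 2.1, two-sided alpha 0.05, power 80%, 17 required per group, 20% attrition, 23 recruited per group. From the post hoc list: Tukey HSD with three arms.

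**The plan's own figure.** For two means, n = 2 × [SD × (1.960 + 0.842) / difference]² = 2 × (2.1 × 2.802 / 2.0)² = 17.3 per group. This agrees with the stated 17 (18 if rounded up). For attrition, 18 / 0.8 = 22.5, so 23. In the other direction, 23 × 0.8 = 18.4, so 17 to 18 evaluable per arm is the planning case and 23 is the case of no dropout.

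**Chance that two arms share a subset.** Assume Tukey is applied to NPRS at one visit with n evaluable per arm.

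- Error degrees of freedom: 3(n − 1).
- Two arms are separated when their observed difference exceeds the half-width q × SD / √n, where q is the 95% point of the studentized range for three groups.
- The chance of not being separated comes from the noncentral t distribution with noncentrality (true difference) / (SD × √(2/n)) and critical value q/√2.

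For example, at n = 18: q = 3.414, half-width = 3.414 × 2.1 / √18 = 1.69, and noncentrality = 2.0 / (2.1 × √(2/18)) = 2.0 / 0.70 = 2.857 against a critical value of 3.414 / √2 = 2.414.

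| Evaluable per arm | q | Half-width (points) | True gap 2.0 | True gap 1.5 | True gap 1.0 |
|---|---|---|---|---|---|
| 17 | 3.420 | 1.74 | 36% | 62% | 84% |
| 18 | 3.414 | 1.69 | 33% | 60% | 83% |
| 23 | 3.391 | 1.48 | 20.5% | 49% | 78% |

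The last three columns give the chance of sharing a subset. A simulation of 40,000 trials per configuration gave the same results for the 2.0-point gap. Requiring a significant overall F test first changed them little (36–37%, 33–34% and 21%).

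**Dependence on how Tukey is applied.** The plan does not say whether Tukey is run at one visit or on a mean over visits, and the documents list different sets of visits (three in the within-group analysis, four at the end of Outcome measures). For a mean over m visits with between-visit correlation r, the SD becomes 2.1 × √[(1 + (m − 1)r)/m], and the 2.0-point gap is diluted to 2.0 × (visits with an effect)/m. The documents give no correlation; I assume 0.3 to 0.7.

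| Quantity compared | 17 per arm | 23 per arm |
|---|---|---|
| Mean of 3 visits including baseline, effect at 2 | 45–63% | 29–49% |
| Mean of 4 visits including baseline, effect at 3 | 28–52% | 14–36% |
| Mean of 2 post-baseline visits | 16–28% | 6–14% |

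**What the label conceals.** Take 23 per arm, the most favourable case, with an observed SD of 2.1. An observed gap of 1.4 points is below 1.48, so the two arms share a subset. The simultaneous 95% interval runs from 1.4 − 1.48 = −0.08 to 1.4 + 1.48 = 2.88 points. An observed gap of 0.5 also gives a shared subset, but its interval ends at 0.5 + 1.48 = 1.98. Both results would carry the same label, although the first leaves 2.0 points well within reach and the second just excludes it.

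**The case against.** The subset analysis is the last item on a post hoc list, after the ANOVA and Tukey's HSD, and no decision rule depends on it. The risk lies in how the result is worded and read. That stands, and it limits the point to wording and reporting.

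A reader might infer that observed power is brought in to support a finding of similarity. The documents do not say so: it sits in a separate paragraph and is not tied to the subsets. It also plays no part in the miss rates above, which follow from the power of Tukey's test at these sample sizes. The criticism of observed power is a separate and lesser one.

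A reader might also infer that the plan would declare the techniques interchangeable or equivalent. No such conclusion is planned. The documents use a word for similarity and leave it undefined.

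Nor can one say without conditions that a real two-point difference would be missed one time in three. That holds for 17 to 18 evaluable per arm and a single-visit test. It is about one in five with all 23 analysed, and across the assumptions shown the rate runs from about 6% to 63%.

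Finally, not every small observed gap leaves 2.0 points open. A gap of 0.5 does at 18 per arm with the Tukey interval (0.5 + 1.69 = 2.19). It does not at 23 per arm (1.98), nor at 18 per arm with an unadjusted 95% interval (0.5 + 1.41 = 1.91). This is a reason to report the interval, since subset membership hides the distinction.

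**Conclusion.** The point holds in a limited form and should be acted on. As written, the plan treats failure to separate arms as similarity, in a trial sized only to detect a difference and with nothing specified that could support such a claim. At a single visit with SD 2.1, a true 2.0-point difference would end in a shared subset 36%, 33% or 20.5% of the time at 17, 18 or 23 evaluable per arm. These rates rest on the plan's own difference and SD, and on a single-visit reading that the plan neither states nor rules out. The fault itself does not depend on dropout: with full follow-up, a gap of 1.4 points would be called similar although the data would be compatible with nearly 2.9. Observed power should go because it is uninformative; the documents do not make it part of the similarity claim.

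**What to change.** 1. Delete the homogeneous-subset analysis. At the least, describe arms that share a subset as not significantly different and not as similar.
2. Drop observed power.
3. Report every pairwise between-arm difference in NPRS points with its Tukey simultaneous 95% confidence interval, and state which visit, or which mean over visits, the comparison uses.
4. Do not conclude similarity unless the whole interval lies inside a margin that is pre-specified, justified and smaller than the plan's 2.0-point relevant effect. A margin as wide as 2.0 would allow arms to be called similar with intervals reaching almost that effect. Otherwise report the comparison as inconclusive.

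The cost is a revision of the SAP text and a little analysis work, plus the effort of justifying a margin if a similarity claim is wanted. No further patients or visits are needed. The downside is that the trial may have to report an inconclusive comparison.

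### Partial eta squared is the only effect measure named, and the plan commits to no NPRS difference with a confidence interval to read against its own 2.0-point target

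*Combined protocol and SAP*

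**What the plan says.** The Sample size calculation section takes NPRS pain as the outcome and states "an expected clinically relevant effect size of 2.0", with an SD of 2.1, two-sided alpha 0.05 and 80% power. It concludes that "the required sample size per group was 17 participants", and then: "Anticipating a 20% attrition rate, we adjusted the sample to 23 participants per group".

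In the Statistical analysis plan, the between-group analysis is a mixed repeated-measures ANOVA with main effects of time and group (three levels) and their interaction. Follow-up tests are Tukey HSD between groups, Bonferroni-adjusted pairwise comparisons for within-subject effects, and homogeneous subsets. Descriptive statistics are means with SDs or medians with IQRs, according to distribution.

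Under Effect size and power, partial eta squared "will be reported to estimate the effect size", and observed power is added where appropriate. Significance is judged by a two-sided p of 0.05 or less. The plan specifies no between-group difference, no confidence interval and no comparison with 2.0 as an output.

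**The concern.** The term effect size carries two meanings. In the sample size it is a distance in NPRS points between two arms. In the analysis plan it is a share of variance across three arms. The second cannot be converted to the first without knowing the pattern of the three means and, in the repeated-measures model, the correlation between visits.

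The first specific objective asks whether application site influences pain and function. All three arms receive active therapy, so a small difference is a plausible result. A non-significant result would then need an interval showing whether 2.0 points has been excluded, and a significant one would need an estimate showing whether 2.0 points was reached. A p-value, partial eta squared and observed power give neither.

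**Working it through.** **Inputs.** From the Sample size calculation section: target 2.0 (no unit given), SD 2.1, alpha 0.05 two-sided, power 80%, 17 evaluable and 23 enrolled per arm. From the SAP: three groups, and visits at baseline, 2 months and 4 months (listed under the within-group analysis). Assumed, because the documents do not give them: equal baseline means, the same gap at both follow-ups, SD 2.1 at every visit, and an equal between-visit correlation ρ of 0.2, 0.5 or 0.8.

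**1. The plan's own figure.** n = 2 × [2.1 × (1.960 + 0.842) / 2.0]² = 17.3 per group, against the stated 17. (Rounded up this is 18, and 18/0.80 = 22.5 gives the stated 23; the rounding does not affect this point.) Read as a standardised effect, 2.0 would need 2 × [(1.960 + 0.842) / 2.0]² = 3.9, or 4 per group. So 2.0 must be NPRS points between two arms.

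**2. One-way partial eta squared for a largest gap of 2.0 points.** η² = f²/(1 + f²), with f² = variance of the three means / 2.1².
- Means 0/0/2: 0.889/4.41 = 0.202, so η² = 0.168.
- Means 0/1/2: 0.667/4.41 = 0.151, so η² = 0.131.
- Means 0/2/2 and 0/0/−2 also give 0.168. One arm worse and one arm better cannot be told apart.

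**3. The planned mixed ANOVA.** The group effect uses each participant's mean over three visits. Baseline contributes no gap, so every between-arm difference shrinks by 2/3: 2.0 × 2/3 = 1.33 points. The variance of the group means becomes 0.889 × 4/9 = 0.395 (0/0/2) or 0.667 × 4/9 = 0.296 (0/1/2). The variance of a participant's mean is 4.41 × (1 + 2ρ)/3.

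For time × group, with S the sum of squared deviations of the three means (2.667 or 2.0), η² = (2S/3) / [2S/3 + 6 × 4.41 × (1 − ρ)].

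| ρ | Group, 0/0/2 | Group, 0/1/2 | Time × group, 0/0/2 | Time × group, 0/1/2 |
|---|---|---|---|---|
| 0.2 | 0.161 | 0.126 | 0.077 | 0.059 |
| 0.5 | 0.119 | 0.092 | 0.118 | 0.092 |
| 0.8 | 0.094 | 0.072 | 0.251 | 0.201 |

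The same 2.0-point gap gives about 0.07 to 0.16 for group and 0.06 to 0.25 for time × group.

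**4. Upward bias.** With identical arms, the expected value is 2/(N − 1): 2/68 = 0.029 at 23 per arm and 2/50 = 0.040 at 17. At the design effect, simulated one-way estimates average 0.191 (true 0.168) and 0.155 (true 0.131) at 23 per arm, and 0.200 and 0.165 at 17. The excess is about 0.02 at 23 per arm and 0.03 at 17.

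**5. What an interval would deliver.** For one visit, SD 2.1 and no baseline adjustment, the standard error of a pairwise difference is 2.1 × √(2/n). The Tukey-adjusted 95% half-width is ±1.48 points at 23 per arm and ±1.74 at 17 (unadjusted: ±1.24 and ±1.45). An observed difference below 2.0 − 1.48 = 0.52 points at 23 per arm, or 2.0 − 1.74 = 0.26 at 17, would exclude 2.0.

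**The case against.** The strongest reply is that partial eta squared is not the whole between-group analysis. Tukey HSD works on signed mean differences in NPRS points, the homogeneous subsets order the arms, and descriptive means are planned. A reader might infer from the effect-size sentence that the trial could not say which technique is better, or could say nothing about 2.0 points. The documents do not support that: pairwise tests are planned, and raw differences could be derived from arm means if those are published.

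What remains is narrower. Tukey HSD is named only as a test, with no estimate or interval promised. The descriptive section does not commit to summaries by arm and visit, and may give medians, which do not yield a mean difference. Tukey contrasts on the mixed-model group effect also average over baseline, so they address about 1.33 points when the true follow-up gap is 2.0.

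A second reply is that the upward bias is small and no decision rule uses partial eta squared. This stands. A reader might infer that the bias materially overstates how far the techniques differ. The one-way excess of 0.02 to 0.03 does not show that, and its relative size should not be carried over to the mixed model, where the true values differ. The case rests on sign, units and mapping, which are limitations at any sample size.

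**Conclusion.** The point holds as an omission of prespecified estimates, not as a fault that invalidates the tests. The plan sizes the trial on 2.0 NPRS points but commits to no output that shows whether 2.0 points was reached or excluded at a follow-up visit. Its one named effect measure has no fixed value for that gap.

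Reading 2.0 as NPRS points between two arms is an inference, but the sample size cannot be reproduced otherwise. The mixed-model ranges and the 1.33 figure rest on the assumptions listed with the calculation. In particular, the ANOVA is taken to use the three visits in the SAP. If it also included the post-third-session visit listed under Outcome measures, with the same gap at all three follow-ups, the averaged gap would be 2.0 × 3/4 = 1.5, still short of 2.0.

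It might also be inferred that the planned model already contains the missing estimates and only needs them printed. It does not: baseline enters as a level of the outcome, so the model gives no baseline-adjusted difference at a visit.

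**What to change.** Name one follow-up visit for the primary comparison. At that visit, prespecify the pairwise between-arm differences in NPRS points, and likewise in WOMAC points, from a model with the baseline score as covariate, with multiplicity-adjusted 95% confidence intervals. State that the NPRS intervals will be read against 2.0 points, and give the unit of that target in the sample size text. Keep partial eta squared as a supplementary description.

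The cost is one additional ANCOVA-type model in SPSS on data already collected, plus SAP wording. No extra participants or visits are needed. The report will show its uncertainty more openly: about ±1.5 points at 23 per arm and ±1.7 at 17 before baseline adjustment, narrower to the extent that baseline predicts follow-up.
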